3.5 Duration of Study

The total duration of treatment is approximately 12 months (eg, 48-54 weeks) for each subject.

The end of the study is defined as the last assessment for the last subject in the study.

The total duration of the study and duration of study treatment for individual subjects may be affected by a pandemic, epidemic, or other emergency not related to the study as described in Section 2.3 of [Appendix 3](#).

4 SELECTION OF STUDY POPULATION

The specific eligibility criteria for selection of subjects are provided in [Section 4.1](#) and [Section 4.2](#). The sponsor will not grant any eligibility waivers.

4.1 Inclusion Criteria

Each subject eligible to participate in this study must meet all the following criteria:

1. Aged 1 to < 4 years at randomization.
2. Written informed consent from the legal guardian/parent (or both parents where required by local authorities). Provide assent where required and as appropriate per local requirements.
3. Sensitivity to peanut, defined as one of the following:
 - a. No known history of peanut ingestion and has serum IgE to peanut ≥ 5 kUA/L within 12 months before randomization.
 - b. Documented history of physician-diagnosed IgE-mediated peanut allergy that includes the onset of characteristic* signs and symptoms of allergy within 2 hours of known oral exposure to peanut or peanut-containing food, and has a mean wheal diameter on skin prick test (SPT) to peanut of at least 3 mm greater than the negative control (diluent) or serum IgE to peanut ≥ 0.35 kUA/L, obtained within 12 months before randomization.

*Characteristic signs and symptoms of IgE-mediated allergic reactions are generally objective and affect the target organs of skin, GI tract, upper/lower respiratory tract, cardiovascular system, or a combination of target organs as follows:

System	Examples of Symptoms (Sampson, 2014)
Cutaneous	Pruritus, erythema/flushing, urticaria, angioedema, contact urticaria
Ocular	Pruritus, tearing, conjunctival injection, periorbital edema
Upper respiratory tract	Pruritus, nasal congestion, rhinorrhea, sneezing, hoarseness, laryngeal edema
Lower respiratory tract	Cough, wheezing, dyspnea, chest tightness/pain
Gastrointestinal	Oral pruritus, oral angioedema (lips, tongue, or palate), colicky abdominal pain, nausea, emesis, diarrhea
Cardiovascular	Tachycardia, dizziness, hypotension, loss of consciousness/fainting

4. Development of age-appropriate dose-limiting allergy symptoms after consuming single doses of peanut protein > 3 mg to ≤ 300 mg in a screening DBPCFC.
5. A palatable vehicle food to which the subject is not allergic must be available for administering study product.

4.2 Exclusion Criteria

Each subject eligible to participate in this study must NOT meet any of the following exclusion criteria:

1. History of severe or life-threatening anaphylaxis anytime before the screening DBPCFC.
2. History of hemodynamically significant cardiovascular or renovascular disease, including uncontrolled or inadequately controlled hypertension.

3. History of biopsy-confirmed diagnosis of EoE; other eosinophilic GI disease; chronic, recurrent, or severe gastroesophageal reflux disease (GERD); or symptoms of dysphagia (eg, difficulty swallowing, food “getting stuck”).
4. Recurrent GI symptoms considered clinically significant in the opinion of the investigator.
5. History of a mast cell disorder including mastocytosis, urticaria pigmentosa, chronic idiopathic or chronic physical urticaria beyond simple dermatographism (eg, cold urticaria, cholinergic urticaria), and hereditary or idiopathic angioedema.
6. Moderate or severe persistent asthma (criteria steps 3-6; National Heart, Lung, and Blood Institute [NHLBI], 2007).
7. Mild asthma (criteria steps 1-2; NHLBI, 2007) that is uncontrolled or difficult to control based on NHLBI 2007 criteria.
8. History of high-dose corticosteroid use (eg, 1-2 mg/kg prednisone or equivalent for > 3 days) by any route of administration as defined by any of the following:
 - Steroid administered daily for > 1 month within 1 year before screening
 - One steroid course within 6 months before screening
 - More than 2 steroid courses ≥ 1 week in duration within 1 year before screening
9. History of food protein-induced enterocolitis syndrome (FPIES) within 12 months before screening.
10. Recurrent urticaria.
11. History of failure to thrive or any other form of abnormal growth, or developmental or speech delay that precludes age-appropriate communication.
12. History of chronic disease (except mild intermittent asthma, mild persistent asthma that is controlled, atopic dermatitis, or allergic rhinitis) that is or is at significant risk of becoming unstable or requiring a change in a chronic therapeutic regimen.
13. Unable to discontinue antihistamines and other medications that could interfere with the assessment of an allergic reaction for 5 half-lives of the medication before the screening SPT, first day of dose escalation, and DBPCFCs.
14. Use or anticipated use of a prohibited medication (eg, beta blockers [oral], angiotensin converting enzyme inhibitors, angiotensin receptor blockers, calcium channel blockers, or tricyclic antidepressants), monoclonal antibody, or any other immunomodulatory therapy (including immunosuppressive medications).
15. Treatment with any form of immunotherapy for any food allergy anytime before screening.
16. Participation in another clinical trial within 30 days or 5 half-lives of the investigational product, whichever is longer, before screening.
17. Allergy to oat or rice.
18. Hypersensitivity to epinephrine or any of the excipients in the epinephrine auto-injector.
19. Parent/caregiver unable or unwilling to use epinephrine auto-injectors.
20. Unable to follow the protocol requirements.
21. Any other condition (concurrent disease, infection, comorbidity, or psychiatric or psychological disorders) or reason that may interfere with the ability to participate in the

study, cause undue risk, or complicate the interpretation of data, in the opinion of the investigator or medical monitor.

22. Resides at the same place as another subject in any AR101 interventional trial.

23. Lives in the same household and/or is a family member of a sponsor employee or site staff involved in conducting this study.

5 ENROLLMENT AND STUDY PROCEDURES

Enrollment and general study procedures are summarized in the following subsections. The study periods will include screening and treatment. The treatment period for subjects receiving study product will include initial dose escalation, up-dosing, and maintenance.

The timing of all study procedures is provided in the schedules of activities.

The interactive response system user manual will contain the information needed for registering subject status (eg, assigning subject identification [ID] numbers, indicating screen failure, and end of study).

Enrollment and study procedures may be affected by a pandemic, epidemic, or other emergency not related to the study as described in [Appendix 3](#).

5.1 Screening Period

The 42-day screening period will be from day -42 through day -1. The screening period will commence after signed informed consent and assent (where required) are obtained, followed by assigning a subject ID number and performing screening procedures.

For the purposes of this study, there will be no day 0.

5.1.1 Informed Consent

Study site personnel must explain to parents/guardians of potential study participants all aspects of the study, including all scheduled visits and activities. Study site personnel must obtain signed informed consent and assent (where required) before any study-specific procedures are conducted unless the procedures are part of routine standard of care. The informed consent process must be documented in the subject's source documents ([Section 13.1.3](#)).

5.1.2 Subject Identification Numbers

After obtaining signed informed consent and assent (where required), study site personnel will access the interactive response system to assign a subject ID number for each potential study participant. This unique number will be used to identify the subject for the remainder of the study.

For subjects with written informed consent and assent (where required) who subsequently do not meet eligibility criteria or if consent is withdrawn, study site personnel will document the screen failure or consent withdrawal in the subject's source documents. The documentation will include demographics and medical history, the reason for screen failure, and procedures performed.

5.1.3 Screening Procedures

Screening procedures are listed in [Appendix 4](#). All screening procedures must be completed within 42 days after signed informed consent and assent (where required) are obtained. Screening procedures should be completed early in the window to avoid potential delays due to scheduling issues or intercurrent illness.

The investigator or designee will assess the eligibility of each subject. All screening procedure results and relevant medical, allergy, and food allergen exposure history must be available before eligibility can be determined. All inclusion criteria must be met and none of the exclusion criteria may apply. No eligibility waivers will be granted.

Rescreening may be considered in certain circumstances on a case-by-case basis following approval from the medical monitor. Signed informed consent and assent (where required) must be reobtained before any rescreening procedures are conducted unless the procedures are part of routine standard of care. Screening laboratory and SPT procedures completed at the time of initial screening do not need to be repeated if rescreening occurs within 6 months.

5.2 Treatment Periods

5.2.1 Treatment Period Visit Windows

The combined windows for screening procedures (from signed informed consent/assent to randomization) and start of randomized study treatment must not exceed 42 days. All up-dosing and maintenance study site visits have a visit window of ± 3 days (ie, 3 days before or after the expected visit day). The initial dose-escalation day 1 visit must be within 10 days after the screening DBPCFC. Day 2 should be the next consecutive day after day 1. If circumstances (eg, an intercurrent illness) create a safety risk, day 2 may be delayed up to 7 days after day 1.

Study treatment will continue daily during visit windows. Study product supplies must be considered when scheduling visits.

5.2.2 Randomization Procedures

After confirmation of eligibility, study site personnel will access the interactive response system to assign subjects to randomized study treatment (AR101 or placebo). Randomized study treatment is to begin within 42 days after signed consent/assent and should be the same day as randomization, or within 3 days (inclusive) after randomization if starting the same

day is not feasible (eg, for circumstances such as intercurrent illness or visit scheduling issues).

5.2.3 General Study Visit Procedures

Day 1 will be the first day of randomized study treatment (AR101 or placebo). Study procedures will be performed at each visit according to the schedule of activities ([Appendix 5](#)).

Before administration of the first and any subsequent dose of study product at the study site, the subject's health status must be at baseline state, including no presence of active wheezing, flare of atopic disease (eg, atopic dermatitis), or suspected intercurrent illness. The subject must have fully recovered from any previous illness for at least 3 days, depending on the severity of the illness per investigator assessment.

A study physician must always be readily available during dosing at the study site. Signs and symptoms of an allergic reaction will be evaluated, and monitoring will continue through the end of the observation period as follows:

- Symptoms of allergic reactions will be evaluated per [Section 8.6.1](#).
- The tolerability of study product will be evaluated per [Section 8.6.1.2](#).
- The treatment of allergic reactions and dose adjustment of study product will follow guidelines per [Section 8.6.2](#) and [Section 8.6.3](#).

On the day after each study site visit, site staff will contact the parent/caregiver by telephone to perform the following ([Appendix 5](#)):

- Inquire if any adverse events occurred (including allergy symptoms, GI symptoms, and exposure to food allergen).
- Provide guidance in managing adverse events.
- Remind the parent/caregiver to record the subject's symptoms in the study diary.
- Inquire about compliance with study product dosing.

5.2.3.1 Initial Dose-Escalation Procedures

Initial dose-escalation procedures are listed in [Appendix 5](#). Subjects may have clear liquids or flavored gelatin during the dosing procedures.

Day 1

Subjects will be required to discontinue antihistamines and other medications that could interfere with the assessment of an allergic reaction for 5 half-lives of the medication before the first day of dose escalation.

Study product will be administered in 4 increasing doses in a stepwise manner in 20- to 30-minute intervals as tolerated. The 4 doses and cumulative dose of study product to be consumed on day 1 are shown in [Table 1](#).

Table 1: Study Product Single Doses and Cumulative Dose on Day 1

Dose Number	Study Product Dose (mg)	Cumulative Dose (mg)
1	0.5	0.5
2	1	1.5
3	1.5	3
4	3	6

The time points for study product dosing and assessments of vital signs and allergic reaction are provided in [Table 2](#). Subjects who develop dose-limiting, moderate, or severe allergy symptoms at any dose of study product, or use rescue medications (except ≤ 2 doses of antihistamines, [Section 8.6.3.1](#)) will stop dose escalation and discontinue early from the study ([Section 5.3](#)).

Table 2: Initial Dose-Escalation Day 1 Procedures

Study Product Dose (Timing) Time Point	Administer Study Product	Vital Signs [1]	Assess Allergy Symptoms
Predose		X	
0.5 mg	X		
15-30 min postdose		X	X
1 mg (20-30 min after previous dose) [2]	X		
15-30 min postdose		X	X
1.5 mg (20-30 min after previous dose) [2]	X		
15-30 min postdose		X	X
3 mg (20-30 min after previous dose) [2]	X		
15-30 min postdose		X	X
Approximately every 30 min until at least 90 min after last dose or end of observation per allergy symptoms [3]		X	X

[1] Vital signs include blood pressure, heart rate, temperature, respiratory rate, and oxygen saturation level.

[2] If the previous dose was tolerated ([Section 8.6.1.2](#)). If the subject has dose-limiting, moderate, or severe symptoms at any dose, or requires rescue medications (except ≤ 2 doses of antihistamines, [Section 8.6.3.1](#)), stop dose escalation and discontinue the subject early from the study. If 3 mg is tolerated, the subject will return for a single 1 mg dose on day 2.

[3] The length of observation is based on signs/symptoms of allergic reaction per [Section 8.6.1](#).
Min, minutes.

Day 2

Subjects who tolerate 3 mg study product on day 1 will return to the study site on day 2 to receive a single 1 mg dose under medical supervision. Day 2 should be the next consecutive day after day 1. If circumstances create a safety risk (eg, an intercurrent illness), day 2 may be delayed up to 7 days after day 1. Subjects who tolerate the 1 mg dose with no more than mild allergy symptoms that are not dose-limiting will receive an adequate supply of study product to continue daily dosing at home at 1 mg/day during up-dosing ([Section 5.2.3.2](#)).

Subjects who are unable to return to the study site \leq 7 days after day 1 for day 2 procedures or who develop dose-limiting, moderate, or severe symptoms after consuming the 1 mg dose on day 2, or use rescue medications (except \leq 2 doses of antihistamines, [Section 8.6.3.1](#)), will stop study product dosing and discontinue early from the study ([Section 5.3](#)).

5.2.3.2 Up-Dosing Procedures

Up-dosing procedures are listed in the schedule of activities in [Appendix 5](#).

Up-dosing study site visits are every 2 weeks for approximately 6 months (minimum 24 weeks if up-dosing proceeds without holding or reducing a dose level; maximum 40 weeks).

Up-dosing will begin when subjects begin daily dosing with study product at 1 mg/day at home for 2 weeks. Subjects who tolerate 1 mg/day for 2 weeks will return to the study site to receive a 3 mg dose. Subjects who tolerate the 3 mg dose at the study site will receive study product to continue daily dosing at home with 3 mg/day for a total of 2 weeks. AR101 dose escalations will continue in this manner up to 300 mg/day as shown in [Table 3](#). Dose adjustments may be allowed ([Section 8.6.3](#), [Section 8.6.4](#)).

Subjects able to tolerate 300 mg/day for 2 weeks within 40 weeks will begin maintenance treatment ([Section 5.2.3.3](#)). Subjects will discontinue early from the study if unable to tolerate 300 mg/day for 2 weeks within 40 weeks, or if the dose level cannot be escalated after 3 consecutive failed attempts (with at least 2 weeks between each escalation attempt) ([Section 5.3](#)).

Additional procedures will be performed at the 80 mg and 300 mg up-dosing visits ([Appendix 5](#)).

Table 3: Up-Dosing Dose-Escalation Schedule (3-300 mg)

Dose Number	Study Product Dose (mg)	Interval (weeks)	Increase From Previous Repeated Dose
1	1	2	Not applicable
2	3	2	200%
3	6	2	100%
4	12	2	100%
5	20	2	67%
6	40	2	100%
7	80	2	100%
8	120	2	50%
9	160	2	33%
10	200	2	25%
11	240	2	20%
12	300	2	25%

Up-dosing begins with the first 1 mg/day dose of study product at home.

5.2.3.3 Maintenance Procedures

The maintenance procedures are listed in [Appendix 5](#). The first maintenance visit will occur after 300 mg/day is tolerated for 2 weeks during up-dosing. Maintenance visits will occur every 4 weeks for an overall total of approximately 12 months of treatment. The duration of maintenance treatment may vary from a minimum of 12 weeks to a maximum of 24 weeks depending on the up-dosing interval (24-40 weeks). Dose adjustments may be allowed ([Section 8.6.3](#), [Section 8.6.4](#)).

After the end of maintenance, an exit DBPCFC will be performed ([Section 9.2](#), [Appendix 1](#), [Appendix 5](#)). The 300 mg daily dose of study product must be tolerated for at least 2 consecutive weeks before having the DBPCFC.

5.2.4 Unscheduled Visit Procedures

Unscheduled visit procedures are listed in the schedule of activities. Other study procedures may be performed as clinically appropriate.

Unscheduled visits may be performed anytime to assess or follow up adverse events, or at the request of the subject or investigator. The date and reason for the unscheduled visit must be recorded in the source documentation.

5.3 Early Discontinuation

Early treatment discontinuation is defined as *permanent* cessation of study product administration anytime before completing the exit DBPCFC. Subjects who discontinue early will have early discontinuation procedures approximately 14 days after their last dose of study product according to the schedule of activities ([Appendix 5](#)).

Subjects with unresolved adverse events at early discontinuation or who had GI adverse events of interest ([Section 8.6.6.2.1](#)) will have safety follow-up per [Section 5.5](#).

Temporary treatment interruption (eg, due to an adverse event) will not be considered early discontinuation.

The primary reasons for early discontinuation of study product are listed in [Table 4](#).

Table 4: Primary Reasons for Early Discontinuation

Category Reason	Comment on Criteria
Protocol/ Investigator-Initiated	
Adverse event or intercurrent illness	
Any intolerable adverse event that cannot be ameliorated using adequate medical intervention or that in the opinion of the investigator or sponsor may lead to undue risk if study treatment were continued, such as the following:
 
• Life-threatening symptoms (CoFAR grade 4), including anaphylaxis resulting in hypotension, neurologic compromise, or mechanical ventilation secondary to study treatment or food challenge.• Severe dose-related allergic hypersensitivity symptoms (CoFAR grade 3) that require intensive therapy (per investigator assessment, but may include interventions such as IV epinephrine, intubation, or admission to an intensive care unit) or are recurrent.• Poor control or persistent activation of secondary atopic disease (eg, atopic dermatitis, asthma).• Development of biopsy-documented eosinophilic esophagitis. 
Any adverse event that meets the early discontinuation criteria for study product tolerability or delays as follows:
 
• Tolerability of study product:
– Dose-limiting, moderate, or severe symptoms at any dose on initial dose-escalation day 1 or 2– Dose withheld for > 4 weeks for chronic or recurrent gastrointestinal adverse events at ≤ 20 mg/day– Unable to tolerate the 300 mg/day dose for 2 weeks within 40 weeks of up-dosing• Use of rescue medications:
– Treatment with epinephrine, beta-agonist, oxygen, IV fluids, > 2 doses of antihistamines, and/or glucocorticosteroids at any study product dose on initial dose-escalation day 1 or 2

Category Reason	Comment on Criteria
	
 – Treatment with epinephrine for a third consecutive time for dose-related allergy symptoms during a dose escalation attempt – Treatment with > 2 doses of epinephrine for a single event of dose-related allergy symptoms anytime • Dose adjustment of study product: 
 – Unable to escalate the dose level after 3 consecutive failed attempts with at least 2 weeks between each escalation attempt – Unable to tolerate a reduced dose of study product after 3 attempts at dose reduction after mild or moderate allergy symptoms, or unable to tolerate a reduced dose of study product after 1 attempt at dose reduction after severe symptoms – Missed ≥ 15 consecutive days of study product dosing for any reason (eg, as part of the treatment for an intercurrent adverse event), unless the dose was withheld for chronic or recurrent gastrointestinal adverse events at ≤ 20 mg/day. Missed doses per dose adjustment guidelines in Section 8.6.3.2 are allowed.
Use of prohibited medication	Prohibited concomitant medications are listed in Section 7.4 .
Death	
Investigator decision	Investigators may elect to discontinue a subject's study treatment if they decide it is in the subject's best interest. Select this category if adverse events/intercurrent illness, use of prohibited concomitant therapy, or noncompliance do not apply and the parent/caregiver preferred the subject to continue treatment.
Major noncompliance with protocol	
The medical monitor or investigator may request early discontinuation in the event of a major protocol deviation, lack of cooperation, or noncompliance.
 
Noncompliance with study product is defined as missed doses for > 7 consecutive days (except for management of intercurrent illness) or missed doses for ≥ 3 consecutive days on 3 occasions, unless the dose was withheld for an adverse event or study product dispensing error (Section 8.6.5).

Dropout	
Parent/caregiver or subject decision	Active discontinuation choice by the parent/caregiver or subject. Subjects may permanently discontinue study treatment anytime for any reason.
Sponsor-Initiated	
Sponsor discontinuation of study	The sponsor reserves the right to terminate the study anytime for any reason as described in Section 13.6 . The sponsor will end this study following completion of the study objectives, or earlier if deemed necessary.
Loss to Follow-Up	
Loss to follow-up	Cessation of subject participation without notice or action. Loss to follow-up procedures are described in Section 5.6 .

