8.5 Assessment of Severity (Intensity)

Severity describes the intensity of a specific adverse event (eg, mild, moderate, severe, life-threatening, or death). The particular event may be of relatively minor medical significance (such as severe headache). Severity is not the same as "serious," which is based on subject/event outcome or action criteria.

Investigators will grade the severity of adverse events. The severity of an adverse event is to be recorded on the case report form and in the subject's source documents.

Three different severity grading systems will be used depending on type of adverse event: allergic reactions, anaphylaxis, or all other adverse events. Brief descriptions of the 3 severity grading systems are provided.

Severity of allergic reactions will be graded using the Consortium of Food Allergy Research (CoFAR) grading system (adapted from [Burks, 2012](#)), with scores ranging from 1 (transient or mild discomfort) to 5 (death) ([Table 7](#)).

Table 7: CoFAR Severity Grading System for Allergic Reactions

Grade 1 Mild	Grade 2 Moderate	Grade 3 Severe	Grade 4 Life-Threatening	Grade 5 Death
Transient or mild discomforts (< 48 hours), no or minimal medical intervention/therapy required.	Symptoms that produce mild to moderate limitation in activity, some assistance may be needed; no or minimal intervention/therapy is required. Hospitalization is possible.	Marked limitation in activity, some assistance usually required; medical intervention/therapy required, hospitalization is possible. Parenteral medication(s) are usually indicated.	Extreme limitation in activity, significant assistance required; significant medical/ therapy. Intervention is required; hospitalization is probable.	Death
Symptoms may include pruritus, swelling or rash, abdominal discomfort, or other transient symptoms.	Symptoms may include persistent hives, wheezing without dyspnea, abdominal discomfort/ increased vomiting, or other symptoms.	Symptoms may include bronchospasm with dyspnea, severe abdominal pain, throat tightness with hoarseness, transient hypotension, or other symptoms.	Symptoms may include persistent hypotension and/or hypoxia with resultant decreased level of consciousness associated with collapse and/or incontinence, or other life-threatening symptoms.	

Source: Adapted from [Burks, 2012](#).

CoFAR, Consortium of Food Allergy Research.

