Moderate	
Administer the previous tolerated dose of study product the next day at the study site.
 
 • If no symptoms occur with the reduced dose, continue that dose level for 2 weeks before attempting re-escalation. • If mild symptoms occur at the reduced dose, follow the guidelines for mild symptoms. • If moderate symptoms occur at the reduced dose, give a second reduced dose (1 or 2 dose levels lower) the next day at the study site. 
 – If the second reduced dose is tolerated, continue that dose level for at least 2 weeks before attempting re-escalation. – If mild symptoms occur with the second reduced dose that is assessed as not tolerated, follow the guidelines for mild symptoms. – If moderate symptoms recur at the second reduced dose, discuss early discontinuation with the medical monitor. 
 ▪ If a third reduced dose is considered to be safe after discussion with the medical monitor, give it at the study site under medical supervision. If the dose is assessed as not tolerated, stop study product dosing and discontinue the subject early from the study (Section 5.3). 
In the rare case that a dose with moderate symptoms is assessed as tolerated, follow the guidelines for mild symptoms and provide a brief explanation for the assessment on the case report form.

Severe	
Discuss early discontinuation with the medical monitor. If continuation of study product is considered to be safe, administer a reduced dose at 2 dose levels the next day at the study site under medical supervision. If the reduced dose is tolerated, continue that dose level for at least 2 weeks before attempting re-escalation. If the reduced dose is assessed as not tolerated, stop study product dosing and discontinue the subject early from the study (Section 5.3).

Life-threatening	
Stop study product dosing and discontinue the subject early from the study (Section 5.3).

Assess dose tolerability per [Section 8.6.1.2](#).

[1] Depending on the subject's stage of development, allergy symptoms may be difficult to interpret. Age-appropriate allergy symptoms should be considered when determining the appropriate actions to be taken with study product dosing.

GI, gastrointestinal.

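### During up-dosing and maintenance, anaphylaxis with transient hypotension gets two severity grades and two dosing actions, depending on which table a site reads

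*Combined protocol and SAP*

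**What the plan says.** Five places in the protocol bear on the same event.

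- **Section 5.3, Table 4.** Among the adverse events that may end treatment it lists "Life-threatening symptoms (CoFAR grade 4), including anaphylaxis resulting in hypotension, neurologic compromise, or mechanical ventilation secondary to study treatment or food challenge". The list is introduced as covering intolerable events that cannot be ameliorated, "or that in the opinion of the investigator or sponsor may lead to undue risk if study treatment were continued, such as the following". The next bullet covers "Severe dose-related allergic hypersensitivity symptoms (CoFAR grade 3) that require intensive therapy" or that recur.
- **Section 8.5, Table 7 (CoFAR).** Grade 3 examples are "bronchospasm with dyspnea, severe abdominal pain, throat tightness with hoarseness, transient hypotension, or other symptoms". Grade 4 examples include "persistent hypotension and/or hypoxia with resultant decreased level of consciousness associated with collapse and/or incontinence".
- **Section 8.5, Table 8 (modified EAACI).** This is the scale the section assigns to anaphylaxis. Hypotension falls in grade 3, severe, which is the top grade. There is no life-threatening grade.
- **Section 3.4.** One study suspension criterion describes anaphylaxis in nearly the same terms as Table 4 but labels it modified EAACI grade 3.
- **Section 8.6.3.2, Table 12.** For life-threatening symptoms, dosing stops and the subject leaves the study. For severe symptoms, early discontinuation is discussed with the medical monitor: "If continuation of study product is considered to be safe, administer a reduced dose at 2 dose levels the next day".

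**The concern.** Table 12 sets the dosing action according to severity, so the grade decides whether treatment must stop or may go on. If the protocol grades one reaction in two ways, two sites can each follow the text faithfully and still handle the same child differently after a serious reaction. What is at stake is uniform safety handling in children aged 1 to under 4 years. Consistent severity coding of anaphylaxis in the safety tables is also affected.

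**Working it through.** The check is a comparison of text. Take one case: after a study product dose in up-dosing or maintenance, a child has anaphylaxis with a brief fall in blood pressure. It is not a recurrence, no intensive therapy is needed, and no more than two epinephrine doses are given (Table 4 ends treatment separately above two).

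**1. Do transient hypotension and anaphylaxis overlap?** Yes. Under Section 8.6.1.1, reduced blood pressure after exposure to a known allergen is enough on its own (criterion 3) to make anaphylaxis likely. No minimum duration is given. Table 8 defines hypotension by an age-based systolic limit, also without a duration.

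**2. The two routes.**

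| Step | Route A | Route B |
|---|---|---|
| Grade | Table 4: CoFAR grade 4, life-threatening | Table 7: CoFAR grade 3; Table 8 and Section 3.4: modified EAACI grade 3, severe |
| Table 4 | First example bullet applies | Grade 3 bullet does not apply (no intensive therapy, no recurrence) |
| Table 12 row | Life-threatening | Severe |
| Action | Stop, no discretion | Discuss with the medical monitor; a reduced dose is allowed if judged safe |

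**3. Is the clash only between two scales?** No. Tables 4 and 7 both use CoFAR and differ on transient hypotension. There is also a mismatch of scale: Table 4 attaches a CoFAR grade to anaphylaxis, for which Section 8.5 prescribes modified EAACI. Table 12 does not name the scale behind its rows. If Table 8 alone were used, no anaphylaxis could reach the life-threatening row.

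**4. Where there is no conflict.** On days 1 and 2, severe and life-threatening symptoms both end participation (Table 11, Section 8.6.6.4). Persistent hypotension with a decreased level of consciousness is CoFAR grade 4 under both Table 4 and Table 7.

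**5. Size.** The inputs are 1 severe anaphylaxis among 372 AR101 subjects aged 4 to 17 in ARC003 (Section 1.2.2) and 88 AR101 subjects planned here (Section 10.3).

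- Expected severe anaphylaxis events: 88 × 1/372 = 0.24.
- Largest shift in the AR101 response rate per affected child, since a subject who discontinues counts as a nonresponder (Section 10.5.1): 1/88 = 1.1 percentage points.
- Expected shift: 0.24 × 1.1 = about 0.3 points.

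The count is only a guide. Section 1.2.2 does not say that the ARC003 case involved hypotension, and the children here are younger. If the rate were one to four times as high (an assumed range), the expected count would run from 0.24 to 4 × 88/372 = 0.95, still below one child.

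**The case against.** The best defence is that Table 4 can be read in line with Table 7. Its first bullet is headed by CoFAR grade 4, so the anaphylaxis it names would be only that which reaches grade 4. Transient hypotension would then fall to the grade 3 bullet, which fits the conditional severe row of Table 12. Table 6 lends support: its life-threatening example combines severe anaphylaxis with a grade 4 allergic reaction, so the two scales can run in parallel on one event. This is a possible intention, but Table 4 does not state it. Its hypotension is unqualified, and Section 3.4 attaches almost the same phrase to modified EAACI grade 3. Table 6 also cuts the other way: by pairing severe anaphylaxis with grade 4 it treats them as different things, whereas Table 4 makes anaphylaxis with hypotension grade 4 outright.

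A second defence is that the actions differ less than the labels. Table 4 gives examples under a judgement of undue risk, and the severe row of Table 12 also depends on a safety judgement and involves the medical monitor. That stands in part. It softens the clash in action but not in grade, and once an event is called life-threatening, Table 12 leaves no judgement to make.

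Two stronger readings are tempting and are not supported.

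- **Eligibility.** A reader might infer a contradiction with exclusion criterion 1, "History of severe or life-threatening anaphylaxis anytime before the screening DBPCFC", because Table 4 also mentions food challenges: a child with such a reaction at the screening challenge would be eligible yet already meet a stopping example. But Table 4 governs permanent cessation of study product, and a child at screening has received none. The food challenge wording has a natural use at the two-day exit challenge. Exclusion criterion 21 lets the investigator or medical monitor exclude a child at undue risk.
- **Primary endpoint.** A reader might infer that the inconsistency threatens the primary result, because stopping makes a child a nonresponder. The figures above show the effect is negligible.

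**Conclusion.** The stopping rule contradicts itself for one defined event: anaphylaxis with transient, non-recurrent hypotension that needs no intensive therapy, during up-dosing or maintenance. Table 4 leads to CoFAR grade 4 and a mandatory stop in Table 12. Tables 7 and 8 and Section 3.4 lead to a severe grade and conditional continuation. Table 12 itself assigns actions, not grades; the conflict in grade lies among the other four places. The conclusion rests on reading Table 4's unqualified hypotension as including transient episodes, which is its plain sense. On the ARC003 rate the event is rare, at about 0.24 expected, and that count covers severe anaphylaxis of any kind in older children. The reason to act is uniform handling of a serious reaction across about 25 sites. The documents do not settle which rule was intended, and this review takes no position on it.

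**What to change.** Reconcile Section 3.4 and Tables 4, 7, 8 and 12 so that hypotension during anaphylaxis has one grade on a named scale and leads to one action. In particular:

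- State in Table 4 whether its hypotension wording covers transient episodes, and use the scale that Section 8.5 prescribes for anaphylaxis or explain why another is used.
- State in Table 12 which scale determines the row when the event is anaphylaxis.
- Align the label in Section 3.4 with whatever is decided.

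The sponsor's clinical team decides which rule stands. The cost is protocol wording and a note to sites. The sample size, endpoints and analyses do not change.
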